11.2.3 Sensitivity Analyses of the Primary Efficacy Endpoint

The sensitivity analyses for the primary endpoint will use different approaches to handle prematurely discontinued subjects and missing Final Month MBL volume.

Unless otherwise specified, the analysis dataset used for sensitivity analysis is the full analysis set. Each of the following sensitivity analyses for the primary endpoint will be performed using a logistic regression model including treatment as the main effect and Baseline MBL volume as a covariate to compare each elagolix dose group to placebo.

Unless otherwise specified, subjects who prematurely discontinue study drug due to "lack of efficacy," "requires surgery or invasive intervention for treatment of uterine fibroids," or adverse events will be considered as non-responders.

1. The primary analysis will be repeated with all subjects categorized as responders/non-responders based on observed or imputed MBL volume data only (without taking into account their reasons for premature discontinuation of study drug). Multiple imputation will be performed the same way as in the primary analysis.
2. Last observation carried forward (LOCF): The primary analysis will be repeated with missing Final Month MBL volume imputed using LOCF (instead of multiple imputation) as described in Section 11.2.3.1.
3. Non-responder imputation (NRI): All subjects who have missing Final Month MBL volume will be considered as non-responders. No multiple imputation will be performed.
4. Observed cases: The primary analysis will be repeated with the observed Final Month MBL volume as defined in Section 7.6. Subjects who have missing Final Month MBL volume will be excluded from this analysis.
5. The primary analysis will be repeated using the total MBL volume collected from validated products only. All subjects will be categorized as responders/non-responders in the same manner as done in the primary analysis (i.e., using the multiple imputation described in Section 11.2.2) with exception that all AH data (including that for Baseline MBL volume) are based on the total MBL volume collected from validated products only.

11.2.3.1 Using Last Observation Carried Forward (LOCF) Imputation

For subjects who have missing Final Month MBL volume and are on study drug at least 56 days prior to and including the Reference Day, their second to last 28 days (the preceding 28-day window prior to the Final Month) of observed MBL volume will be

carried forward to the Final Month. If the second to last 28 days of MBL volume is also missing and the subject has at least 84 days prior to and including the Reference Day, her third to last 28 days of observed MBL volume will be carried forward to the Final Month, and so on.

Subjects who have missing Final Month MBL volume and don't have a 28-day observed MBL volume to be carried forward will be excluded from the sensitivity analysis using the LOCF imputation.

11.2.4 Adenomyosis Subset

The proportion of responders and difference in proportions between each elagolix treatment group and placebo will be summarized as in the primary analysis for subjects with Baseline adenomyosis present, and repeated for the subjects with adenomyosis at any time during the Baseline or Treatment Period (see definition in Section 11.3.5.3). No statistical tests will be performed. This will be calculated using the same imputed datasets as in the primary analysis, subset for the subjects identified in the adenomyosis subset of interest.

For each of the adenomyosis subsets defined in Section 11.3.5.3, the statistical comparison between each elagolix dose group and placebo for subjects with Baseline adenomyosis present will be made using a logistic regression model including treatment as the main effect and Baseline MBL volume as a covariate in the integrated summary of efficacy (ISE) setting together data from Studies M12-815 and M12-817. The proportion of responders, difference in proportions between each elagolix treatment group and placebo and odds ratio with corresponding 95% CI, and p-values will be calculated. This will be calculated using the same imputed datasets as in the primary analysis for each respective study, subset for the subjects identified in the adenomyosis subset of interest.

11.3 Ranked Secondary and Other Efficacy Analyses

Ranked secondary efficacy endpoints during the Treatment Period include the following in the order specified below:

1. Change from Baseline in MBL volume to the Final Month;
2. Percentage of subjects with suppression of bleeding (no bleeding allowed, spotting allowed) at the Final Month;
3. Change from Baseline in MBL volume to Month 6;
4. Change from Baseline in MBL volume to Month 3;
5. Percentage of subjects with Baseline hemoglobin ≤ 10.5 g/dL who have an increase in hemoglobin > 2 g/dL at Month 6;
6. Change from Baseline in MBL volume to Month 1.

Other efficacy endpoints during the Treatment Period include the following:

- Change and percent change from baseline in MBL volume;
- Percentage of subjects with MBL volume < 80 mL and 50% or greater reduction in MBL volume from baseline during 28-day intervals throughout the Treatment Period;
- Percentage of subjects with amenorrhea;
- Percentage of subjects with control of bleeding;
- The number of bleeding days;
- Change and percent change from baseline in hemoglobin concentration;
- Patient Global Impression of Change (PGIC) questionnaire for Menstrual Bleeding and Non-Bleeding Uterine Fibroid Symptoms;
- Change and percent change from baseline in fibroid and uterine volume;
- Change from baseline for the UFS-QoL;
- Change from baseline for the EuroQoL-5D (EQ-5D-5L);
- The Health Care Resource Utilization (HCRU) questionnaire;
- Change from baseline for the WPAI.

11.3.1 Reduction of Bleeding

The change and percent change from Baseline to the Final Month in MBL volume obtained from the primary analysis after multiple imputation will be summarized by treatment group and compared between each elagolix dose group and placebo, using one-way ANCOVA with treatment as the main effect and Baseline MBL volume as a covariate. Baseline and Final Month MBL volumes obtained for the primary analysis will be used. This analysis will be used for the first ranked secondary efficacy endpoint: change from Baseline in MBL volume to Final Month.

The change and percent change from Baseline to each 28-day window starting at Study Day 2 up to Study Day 168 in the Treatment Period (i.e., Month 1 (Study Days 2 – 28), Month 2 (Study Days 29 – 56), Month 3 (Study Days 57 – 84), Month 4 (Study Days 85 – 112), Month 5 (Study Days 113 – 140), and Month 6 (Study Days 141 – 168)) in observed MBL volume will be summarized by treatment group and compared between each elagolix dose group and placebo, using one-way ANCOVA with treatment as the main effect and Baseline MBL volume as a covariate. The change and percent change from Baseline to Final Month in observed MBL volume will be performed similarly.

For observed MBL volume in each 28-day interval, only subjects who did not prematurely discontinue in or before this 28-day interval will be included. For example, for Study Days 29 – 56, it includes subjects who were on treatment for at least 56 days.

The comparison of change or percent change from Baseline in MBL volume to each month between each of the elagolix dose groups and placebo will be performed using a Mixed Model Repeated Measures (MMRM) model with observed MBL volume. The MMRM analysis will include the fixed categorical effects of treatment, month and treatment-by-month interaction, and the continuous fixed covariate of Baseline MBL volume. The REPEATED statement will be used for month in PROC MIXED with blocks in the covariance matrix identified by subject nested within treatment group. The following covariance structures will be used model the variance-covariance matrix: Spatial Power, Compound Symmetry, and Unstructured. For each efficacy parameter

(change or percent change from Baseline), the covariance structure converging to the best fit, as determined by the smallest value for the Akaike Information Criterion (AIC), will be used as the covariance structure in the MMRM analysis for that efficacy parameter. This analysis will be used for the ranked secondary efficacy endpoints: change from Baseline in MBL volume to Month 6, Month 3, and Month 1.

Each of the two response criteria that are components of the primary endpoint, i.e., (1) MBL volume of < 80 mL at the Final Month; and (2) 50% or greater reduction in MBL volume from Baseline to the Final Month will be analyzed separately in the same way as for the primary analysis. Baseline and Final Month MBL volumes obtained for the primary analysis will be used. The number and percentage of subjects meeting each criteria at the Final Month will be summarized by treatment group. The comparison between each elagolix dose group and placebo will be made using a logistic regression model including treatment as the main effect and Baseline MBL volume as a covariate.

Besides the method in the primary analysis, the number and percentage of subjects meeting each criterion at the Final Month will also be analyzed in the same way as in each sensitivity analysis for the primary endpoint, and in the analysis for subjects identified in the adenomyosis subset of interest.

The number and percentage of subjects satisfying either (1) MBL volume < 80 mL, or (2) 50% or greater reduction in MBL volume from Baseline, or both will be summarized for every 28-day interval by treatment group based on observed MBL volume.

Plots will be provided by treatment group using the MBL volume data for the primary analysis (multiple imputation):

- Cumulative distribution function for MBL volume at Final Month;
- Cumulative distribution function for percent change from Baseline to Final Month in MBL volume;
- Proportion of responders at Final Month;

- Cumulative distribution function for change from baseline to Final Month in MBL volume.

Plots will be provided by treatment group using observed MBL volume data:

- Cumulative distribution function for change from baseline in MBL volume to Month 1, 3, and 6;
- Mean change in MBL volume over time.

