key bleeding assessments, specific non-bleeding assessments based on a Non-Bleeding Symptoms Uterine Fibroid Questionnaire (NBUFSQ), and other QOL variables including UFS-QOL. The safety and tolerability objectives include the assessment of standard safety parameters, in addition to hypoestrogenic adverse events of interest, including BMD loss as assessed by dual energy x-ray absorptiometry (DXA) and vasomotor symptoms, such as hot flush. Endometrial health via transvaginal ultrasound (TVU) and endometrial biopsy are also evaluated.

Preliminary results from Cohort 1 demonstrated that treatment with elagolix 300 mg BID plus E2/NETA showed the following:

- Robust efficacy in controlling HMB (composite bleeding endpoint of 91.9%, 85.5%, and 79% in the elagolix 300 mg BID alone, elagolix 300 mg BID plus low-dose E2/NETA, and elagolix 300 mg BID plus standard-dose E2/NETA treatment groups, respectively) associated with uterine fibroids
- Clinically meaningful improvement in quality of life measures and symptom severity scores as assessed by UFS-QOL
- Mitigation of BMD loss at the lumbar spine, with standard-dose E2/NETA
- Substantial dose-dependent reduction in the incidence of vasomotor symptoms, e.g., hot flushes
- No evidence of endometrial safety concerns
- Overall safety profile remains unchanged, with no new or unexpected findings to date.

Overall, preliminary findings from the Phase 2b study suggest that standard-dose E2/NETA as add-back therapy may be effective in preventing BMD loss during treatment with elagolix 300 mg BID, with minimal impact on primary efficacy bleeding endpoints in premenopausal women with HMB associated with uterine fibroids. This dosing regimen could potentially meet the objective of a long-term therapy for the management of symptomatic uterine fibroids in premenopausal women.

Preliminary results from Study M12-813 show that all treatment arms (both doses of elagolix [300 mg BID and 600 mg QD] alone or in combination with either strength of E2/NETA) met the primary endpoint, which is the proportion of subjects who achieved an MBL volume of < 80 mL at the Final Month **and** 50% or greater reduction in MBL volume from Baseline to the Final Month compared to that of placebo (all P < 0.001), as measured by the alkaline hematin method.

[figure not shown]
AbbVie Ongoing Phase 3 Clinical Studies

Endometriosis

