3.0 Introduction

This statistical analysis plan (SAP) describes the planned statistical analyses for elagolix (ABT-620) Study M12-815 titled "A Phase 3 Study to Evaluate the Efficacy and Safety of Elagolix in Combination with Estradiol/Norethindrone Acetate for the Management of Heavy Menstrual Bleeding Associated with Uterine Fibroids in Premenopausal Women." The analysis plan was created based on the Study Protocol M12-815 Amendment 3 dated 25 September 2017.

This analysis plan describes both the efficacy and safety analyses. The pharmacokinetic data will be analyzed separately and is not addressed in this SAP.

The SAS System 9.2 or above will be used to perform the statistical analyses. All statistical tests will be two-sided and a significance level of 0.05 will be used unless otherwise specified.

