4.3 Sample Size

Approximately 400 subjects will be randomized in a 1:1:2 ratio to placebo (N = 100), elagolix 300 mg BID (N = 100), or elagolix 300 mg BID plus E2/NETA (N = 200). The sample size will provide at least 90% power to detect a difference between the elagolix 300 mg BID plus E2/NETA group and the placebo group in the percentage of subjects with menstrual blood loss (MBL) volume < 80 mL during the Final Month (as defined in Section 7.2) and 50% or greater reduction in MBL volume from Baseline to the Final Month under the assumption of responder rates being 60% and 30% for elagolix 300 mg BID plus E2/NETA and placebo, respectively. The sample size determination is primarily driven by the need for a sufficient number of patients for the safety database. The above sample size was calculated using nQuery advisor 7.0.

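### The ANCOVA and MMRM for the ranked MBL-change endpoints assume equal variance in all arms, so the SE and 95% CI for E2/NETA versus placebo (200:100) are miscalibrated if arm variances differ

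*SAP*

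**What the plan says.** SAP 11.3 ranks six secondary endpoints. Four are changes in MBL volume: to the Final Month (rank 1), Month 6 (rank 3), Month 3 (rank 4) and Month 1 (rank 6).

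- **Rank 1.** SAP 11.3.1 compares each elagolix group with placebo "using one-way ANCOVA with treatment as the main effect and Baseline MBL volume as a covariate", on the multiply imputed data (20 imputations, SAP 11.2.2.1).
- **Ranks 3, 4 and 6.** SAP 11.3.1 uses an MMRM on observed volumes. The candidate covariance structures are spatial power, compound symmetry and unstructured. The one kept is "the covariance structure converging to the best fit, as determined by the smallest value for the Akaike Information Criterion (AIC").
- **Reporting.** SAP 11.1 has between-group differences reported with SE, 95% CI and p-value.
- **Allocation.** SAP 4.3 sets 1:1:2, that is 100 placebo, 100 elagolix alone and 200 elagolix plus E2/NETA. SAP 11.4 makes E2/NETA versus placebo the primary comparison for all analyses.

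The MMRM blocks are identified by subject within treatment group. That says which observations are correlated; it does not give each arm its own covariance matrix. The unstructured option lets variance differ by month but not by arm. Neither SAP 11.3.1 nor Protocol 8.1.7.2 adds a robust SE, a transformation or an unequal-variance analysis for MBL change. The sensitivity analyses in SAP 11.2.3 concern the responder endpoint.

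**The concern.** There is reason to expect unequal spread. Entry requires more than 80 mL with no upper limit on volume (Protocol 5.2.1), so untreated volumes can be wide and right-skewed. Treatment pushes volume toward a floor: Protocol 3.2.3 reports a Phase 2b "composite bleeding endpoint of 91.9%, 85.5%, and 79% in the elagolix 300 mg BID alone", low-dose E2/NETA and standard-dose E2/NETA groups in that order. SAP 7.6.1.1 sets no-visible-blood, no-bleeding and below-quantitation results to exactly 0, which adds to the pile-up at zero on active treatment.

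A pooled variance is weighted by arm size. Here three quarters of the weight sits on the active arms, while placebo contributes the larger share of the true sampling error because it has only 100 women. If placebo has the larger residual SD, the pooled SE is too small. At stake is the precision claimed for the MBL differences in four of the six ranked endpoints.

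**Working it through.** **The plan's own figure.** SAP 4.3 states "The sample size will provide at least 90% power to detect a difference" "under the assumption of responder rates being 60% and 30% for elagolix 300 mg BID plus E2/NETA and placebo, respectively". With 200 and 100 women and two-sided 0.05:

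- null SE = √(0.5 × 0.5 × (1/100 + 1/200)) = 0.0612
- alternative SE = √(0.3 × 0.7/100 + 0.6 × 0.4/200) = 0.0574
- power = Φ((0.30 − 1.96 × 0.0612)/0.0574) ≈ 99.9%

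This agrees with the stated lower bound. The documents give no SD, SE or power for any MBL-change endpoint, so the rest is a function of an assumed SD ratio.

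**Closed form, three-arm model.** Let k be placebo residual SD divided by active residual SD, with both active SDs set to 1.

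- Pooled variance = (100k² + 100 + 200)/400 = (k² + 3)/4
- Pooled SE² for E2/NETA versus placebo = [(k² + 3)/4] × (1/100 + 1/200)
- True SE² = k²/100 + 1/200
- Coverage of a nominal 95% CI = 2Φ(1.96 × pooled SE/true SE) − 1

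| k | pooled SE² | true SE² | SE ratio | coverage |
|---|---|---|---|---|
| 0.75 | 0.01336 | 0.01063 | 1.12 | 97.2% |
| 1 | 0.01500 | 0.01500 | 1.00 | 95.0% |
| 1.25 | 0.01711 | 0.02063 | 0.91 | 92.6% |
| 1.5 | 0.01969 | 0.02750 | 0.85 | 90.3% |
| 2 | 0.02625 | 0.04500 | 0.76 | 86.6% |
| 3 | 0.04500 | 0.09500 | 0.69 | 82.3% |

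**Pairwise model.** SAP 11.3.1 does not say whether the ANCOVA is fitted to all three arms or pair by pair. For E2/NETA versus placebo alone (200:100), coverage is 91.5% at k = 1.5 and 89.0% at k = 2.

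**Elagolix alone versus placebo (100:100).** In the three-arm model at k = 2, pooled SE² = 1.75 × 0.02 = 0.035 and true SE² = 0.04 + 0.01 = 0.05. The SE ratio is 0.84 and coverage 89.9%. In a pairwise model, pooled SE² = [(k² + 1)/2] × 0.02 equals true SE² = (k² + 1)/100, so coverage is 95% at any k.

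**Which way k goes.** Assumed lognormal MBL distributions, some with a share of exact zeros on active treatment, were tuned to given responder rates over a grid of 108 scenarios per set, with large-sample variances from the ANCOVA. Placebo response was set at 30%, which for the Phase 2b set is an assumption.

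| active response | pooled SE too small | median coverage | range |
|---|---|---|---|
| Phase 2b (91.9% alone, 79% with E2/NETA) | 90% of scenarios | 86% | 78% to 97% |
| design (60% in both) | 44% of scenarios | 97% | 80% to 99.7% |

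**Finite samples.** In simulated three-arm ANCOVAs of 100/100/200 at the Phase 2b active rates (placebo response assumed at 30% or 10%), pooled CIs for E2/NETA versus placebo covered 89% to 93%. HC3 robust CIs covered 94% to 95%.

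The MMRM was not simulated, and the simulations did not include the multiple imputation step. For ranks 3, 4 and 6 the argument rests on the shared covariance structure, not on a coverage figure for the planned model.

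**The case against.** Common-variance ANCOVA and MMRM are conventional prespecified choices, and four objections have force.

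1. **The p-values.** A reader might infer that the fixed sequence is anti-conservative in four of six ranked tests. The documents do not support that. If treatment does nothing, the arms share one distribution, variances are equal and the test is valid. With identical skewed arms (four cases, 3,000 runs), the pooled test rejected in 4.5% to 5.7% and HC3 in 4.2% to 5.4%. At Phase 2b active rates the two methods rejected almost equally often. P-values would be anti-conservative only under equal means with unequal variances. This objection stands.

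2. **The direction.** A reader might infer that the SE is known to be too small. No MBL SD is given for either arm. At the design rates the pooled SE was more often too large, because a long upper tail in active non-responders can make the active arms the more variable ones. This stands against a one-directional claim. It does not rescue the pooled SE, which is then wrong the other way.

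3. **The scope.** The problem is clearest for E2/NETA versus placebo. It is smaller for elagolix alone and absent there in a pairwise model. This stands.

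4. **The remedy.** Robust SEs are not a cure under very heavy tails: in two such design-rate simulations HC3 covered 91% and 89%, against 97.5% and 96% pooled. An unstructured matrix over six months has 6 × 7/2 = 21 parameters, and 63 if fitted separately in three arms, so convergence needs a plan. This stands as a limit on the fix.

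The by-arm distribution plots planned in SAP 11.3.1 would display unequal spread but would not correct an interval.

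**Conclusion.** The point holds as a matter of CI calibration for the secondary MBL estimates. Both models impose one variance or covariance on all arms in a setting where the drug is expected to change the spread, and the 200:100 allocation turns any such difference into a wrong SE for the main comparison.

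If placebo is the more variable arm, nominal 95% CIs for E2/NETA versus placebo cover about 93%, 90% and 87% at SD ratios of 1.25, 1.5 and 2. Those figures assume a three-arm ANCOVA, equal active SDs and large-sample normality. The Phase 2b response rates make that direction plausible; the documents do not establish it, and at 60% versus 30% it can reverse.

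The primary logistic analysis is not affected, and a large MBL effect would probably remain significant under either SE. This is a change worth making before analysis, not a threat to the trial's main conclusion.

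**What to change.** In SAP 11.3.1:

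- **ANCOVA (rank 1).** Use heteroscedasticity-consistent SEs, or residual variance by treatment group (PROC MIXED, REPEATED with GROUP=treatment). Combine over the 20 imputations by Rubin's rules. State whether the model is three-arm or pairwise.
- **MMRM (ranks 3, 4 and 6).** Use the EMPIRICAL (sandwich) option, or add GROUP=treatment structures to the candidates with a stated fallback if they do not converge.
- **Sensitivity analysis.** Keep the common-variance models, so that readers can see how much the variance assumption matters.

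The cost is a few SAP sentences and standard SAS options, with no new data. Intervals may be slightly wider, by-arm covariance needs the fallback rule, and robust SEs do not fully restore coverage under very heavy tails.

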8.1.7.2.1 Reduction of Bleeding

The percentage of subjects with MBL volume < 80 mL and 50% or greater reduction in MBL volume from baseline during the Treatment Period will be summarized for each treatment group and compared between each elagolix treatment group and the placebo group. Also, the individual component (the percentage of subjects with MBL volume of

< 80 mL as well as the percentage of subjects with \geq 50% in MBL volume reduction from baseline) will be summarized.

The change and percent change from baseline in MBL volume to each month and to the Final Month, will be summarized for each treatment group and compared between each elagolix treatment group and the placebo group.

The percentage of subjects with suppression of bleeding and the percentage of subjects with amenorrhea will be summarized by monthly intervals throughout the Treatment Period. For each subject, suppression of bleeding will be defined as having no days of bleeding (spotting is allowed) during a 28-day interval. Amenorrhea is defined as having no days of bleeding or spotting during a 28-day interval. In addition, the cumulative percentage of subjects with suppression of bleeding and the cumulative percentage of subjects with suppression of bleeding and the cumulative percentage of subjects with amenorrhea will be compared between each elagolix treatment group and the placebo group.

[figure not shown]
The change and percent change from baseline to monthly intervals in number of bleeding days will be summarized by treatment group. In addition, the change from baseline in total number of sanitary products will be summarized and compared between each elagolix treatment group and the placebo group.

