7.0 Analysis Conventions

7.1 Definition of Baseline

Unless otherwise specified below, Baseline for a variable will be defined as the last non-missing value obtained prior to or on Study Day 1.

MBL Volume Baseline

Baseline MBL volume will be defined as the mean of total MBL volume from all the qualified menstrual cycles during the Screening Period, in which the total MBL volume is from all validated and non-validated sanitary products that subjects returned and where the MBL volume of validated sanitary products only (excluding non-validated sanitary products) is greater than 80 mL. All menstrual cycles during the Screening Period in which the total MBL of all validated products is less than or equal to 80 mL will not be included in the Baseline MBL volume calculation. If the gap between two consecutive Screening menstrual cycles is 1 day apart or less (i.e., out of the two consecutive cycles, the start date of the second cycle – the end date of the first cycle ≤ 2), these two Screening menstrual cycles will be combined as one Screening menstrual cycle for the calculation of Baseline.

Bleeding Days Baseline

Baseline for bleeding days (as defined in Section 7.6) will be the mean of total number of bleeding days over all the qualified Screening menstrual cycles that are used to calculate Baseline MBL volume.

Fibroid and Uterine Volume Baseline

Baseline for uterine volume, volume of the largest fibroid, total fibroid volume (3 largest fibroids), and endometrial thickness measured by ultrasound (transvaginal [TVU] or transabdominal [TAU]) or Magnetic Resonance Imaging (MRI) will be based on the last non-missing measurement collected during the Screening Period. If there is no measurement collected on or prior to Study Day 1, the first measurement collected prior to Study Day 8 (Study Day 8 is not included) will be used as Baseline.

Adenomyosis Baseline

Baseline for adenomyosis measured by TVU/TAU or MRI will be based on the last non-missing measurement collected on or prior to Study Day 1. If there is no measurement collected on or prior to Study Day 1, the first measurement collected prior to Study Day 15 (Study Day 15 is not included) will be used as Baseline.

Quality of Life Questionnaires Baseline

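### The monthly responder endpoint is defined as meeting both bleeding criteria, but SAP 11.3.1 describes its only monthly summary as meeting either one or both

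*SAP*

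**What the plan says.** The SAP lists the monthly endpoint among the other (unranked) efficacy endpoints in 11.3: "Percentage of subjects with MBL volume < 80 mL and 50% or greater reduction in MBL volume from baseline during 28-day intervals". Protocol 8.1.7.2 lists the same endpoint. Protocol 8.1.7.2.1 repeats the joint condition, "The percentage of subjects with MBL volume < 80 mL and 50% or greater reduction in MBL volume from baseline during the Treatment Period", and says that this percentage will be summarized and compared between each elagolix group and placebo. It then adds the two criteria as extra summaries: "Also, the individual component (the percentage of subjects with MBL volume of" less than 80 mL, and likewise the percentage with the 50% reduction.

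SAP 11.3.1 is where the monthly analysis is described. Its one sentence on monthly response counts women "satisfying either (1) MBL volume < 80 mL, or (2) 50% or greater reduction in MBL volume from Baseline, or both". The output is a descriptive table: this count "will be summarized for every 28-day interval by treatment group based on observed MBL volume". The sentence mentions no comparison with placebo.

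The primary endpoint in SAP 11.2.1 requires both conditions at the Final Month and is not in question.

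**The concern.** The definition says *and*; the analysis sentence says *either, or, or both*. Taken at face value, the analysis sentence produces a percentage for a different event and leaves the listed endpoint with no described analysis. The end-of-treatment analyses are to be run by an external Independent Data Analysis Center (SAP 4.4), so the wording has to stand on its own.

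What is at stake is a table that does not match its label. For a woman who completes treatment, Month 6 (Days 141 to 168) largely overlaps the Final Month. The report could then show two response rates for nearly the same four weeks, one requiring both criteria and one requiring either. A reader following response over time would take the monthly series as the path to the primary result, and it would not be.

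**Working it through.** **1. The plan's own figure.** The documents state no monthly rate under either rule. The nearest figures are the planning rates for the Final Month composite: "under the assumption of responder rates being 60% and 30% for elagolix 300 mg BID plus E2/NETA and placebo", respectively, with subjects "randomized in a 1:1:2 ratio to placebo (N = 100), elagolix 300 mg BID (N = 100") and 200 on the combination. With pooled rate (0.6×200 + 0.3×100)/300 = 0.50, the null SE is √(0.25×(1/200 + 1/100)) = 0.0612. The SE under the alternative is √(0.24/200 + 0.21/100) = 0.0574. Power = Φ((0.30 − 1.96×0.0612)/0.0574) = Φ(3.13) = 99.9%, so the stated floor of 90% holds. These rates refer to the *both* rule.

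**2. The two rules as thresholds.** Let B be Baseline MBL and y the MBL in a 28-day window.

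- Both criteria: y < 80 and y ≤ B/2, that is, below the smaller of 80 and B/2.
- Either criterion: y < 80 or y ≤ B/2, that is, below the larger.

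B always exceeds 80 mL, because only screening cycles enter "where the MBL volume of validated sanitary products only (excluding non-validated sanitary products) is greater than 80 mL" (SAP 7.1). The two thresholds coincide only at B = 160 mL.

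**3. What is lost, by Baseline.**

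- For 80 < B < 160, the either rule is just y < 80. The reduction needed falls from 50% to just over 1 − 80/B: 6% at B = 85, 11% at 90, 20% at 100, 33% at 120. A fall from 95 to 79 mL is 16/95 = 17% and counts.
- For B > 160, the 50% reduction is still required and the 80 mL cap disappears. A fall from 300 to 150 mL counts, although 150 mL is nearly twice the heavy-bleeding limit.

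**4. Direction.** P(either) = P(1) + P(2) − P(both). Since P(1) and P(2) are each at least P(both), P(either) ≥ P(both) in every arm, whatever the data.

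**5. Size with no treatment effect (assumptions, not document figures).** Assume a lognormal month with median B and within-woman log-SD 0.4. The chance of y ≤ B/2 is Φ(ln 0.5/0.4) = 4.2%, and the chance of y < 80 is Φ(ln(80/B)/0.4).

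| B (mL) | Both | Either |
|---|---|---|
| 85 | 4.2% | 44% |
| 100 | 4.2% | 29% |
| 120 | 4.2% | 16% |
| 160 | 4.2% | 4.2% |
| 200 | 1.1% | 4.2% |
| 300 | 0.05% | 4.2% |

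Averaged over a simulated screened population (two screening cycles above 80 mL, a third if needed; median 120–220 mL; between-woman log-SD 0.5–0.7):

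- Within-woman log-SD 0.3–0.8: both 0.8%–24%, either 5.5%–42%, ratio 1.8 to 7.3.
- Middle case (median 180 mL, log-SD 0.4): about 4% against 14%, ratio about 3.7.
- Log-SD 0.2: ratio above 30, only because the *both* rate is about 0.1%–0.2%.
- If 5–20% of windows have no bleeding (median 180 mL, log-SD 0.3–0.5): ratio 1.2 to 2.2.

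**6. Size tied to the plan's rates.** Take 30% as the placebo rate for both criteria in a month. The either rate cannot pass 100%, so the ratio is at most 1/0.30 = 3.3. For the combination at 60% it is at most 1/0.60 = 1.7. Simulations calibrated to 30% give an either rate of 35%–72%, a ratio of 1.15 to 2.4. The lower end comes from adding no-bleeding windows, the upper end from shifting all volumes down.

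**The case against.** The best defence is that the sentence lists table rows: criterion (1), criterion (2), and both. That would match the protocol's composite plus individual components. The endpoint list and the primary definition both use *and*, so the intended endpoint is not really in doubt. This reading is possible, and the SAP does not exclude it. But the sentence describes a single number and percentage, and two paragraphs earlier the same section says explicitly that the two Final Month criteria are analyzed separately. The ambiguity therefore remains.

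The defence is right about consequence. The table is descriptive, uses observed data, lies outside the fixed sequence in SAP 11.4, and applies one rule to all arms, so women who respond by chance would also appear under placebo.

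A reader might infer three stronger things that the documents do not support:

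- *That the 50% requirement is abandoned altogether.* It is relaxed only for Baseline between 80 and 160 mL. The 300 to 150 mL case is a full 50% reduction.
- *That the no-effect response rate rises several-fold.* That depends on assumed variability, and the ratio can be as low as about 1.2.
- *That there is a false-positive problem.* No error-controlled test uses this table.

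On the missing comparison, SAP 11.1 says in general terms that each elagolix group is compared with placebo on efficacy variables. The gap is thus chiefly an unnamed method.

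**Conclusion.** The mismatch between definition and analysis sentence is real and should be corrected. Read literally, SAP 11.3.1 reports the union of the two criteria, gives a percentage that does not answer the listed endpoint, and leaves that endpoint without a described analysis. Read generously, it is unclear. The direction is certain: the union rate is never lower and will generally be higher in every arm. The size is not settled by the documents, which give neither the Baseline distribution nor the cycle-to-cycle variability. The firm statement is the ceiling of 3.3-fold at a 30% placebo rate, and that borrows the Final Month planning rate for a single month. Whether the contrast between arms would widen or narrow cannot be determined from the documents. The primary endpoint, its type I error and its power are untouched. This is a consistency defect in a secondary table, worth fixing because it costs almost nothing.

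**What to change.** Replace the sentence in SAP 11.3.1 with wording such as:

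> For each 28-day interval and treatment group, using observed MBL volume, report the number and percentage of subjects meeting both (1) and (2), and separately the number and percentage meeting (1) and meeting (2). The percentage meeting both will be compared between each elagolix group and placebo by logistic regression with treatment and Baseline MBL volume.

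The model is the one already used for the primary endpoint. The Pearson or Fisher test used for other binary outcomes in SAP 11.3.2 would also serve, provided that one is named. The comparison should be confined to the composite: Protocol 8.1.7.2.1 asks for the individual criteria to be summarized only.

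Nothing is lost by the change. The union can be recovered as (1) + (2) − both, whereas the composite cannot be recovered from the union alone. The cost is a wording edit and the matching table shell, with no new data and no effect on sample size.
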